##### **6.2 Intention-to-Treat (ITT)**

The Intention-to-Treat will include all subjects who are randomized regardless of exposure to test article. The ITT population will include subjects who did not present with stage 2 or 3 NK at the screening visit per the CRC but exclude subjects who have no post-baseline images. Subjects will be classified according to the treatment at randomization. The ITT population will be used as a supplemental analysis for evaluating the primary endpoint.

##### **6.3 Per-protocol Set (PPS)**

The per-protocol set will be a subset of FAS, excluding subjects who have any major protocol deviation which is likely to seriously affect the safety and efficacy outcomes of the study.

Evaluability will be assessed by subjects, visits and study procedures. The per-protocol set will be used to evaluate the primary efficacy endpoints as exploratory analyses.

#### **6.4 Safety Analysis Set**

The safety analysis set for the controlled phase will include all subjects who are randomized that receive at least one dose of test article in the controlled phase of the study. Subjects will be classified according to the treatment assigned at randomization unless the incorrect treatment(s) are received throughout the dosing period in which case subjects will be classified according to the first treatment received. The safety analysis set will be the primary population for evaluating treatment compliance and safety for the controlled phase of the study.

#### **6.5 Safety Analysis Set – Uncontrolled phase**

The safety analysis set for the uncontrolled phase will include all subjects who enter the uncontrolled phase and receive at least one dose of test article in the uncontrolled phase of the study. The safety analysis set for the uncontrolled phase will be the primary population for evaluating all uncontrolled phase data.

### **7.0 GENERAL STATISTICAL CONSIDERATIONS AND DEFINITIONS**

#### **7.1 General Consideration and Table Layout**

The controlled phase data will be evaluated when all subjects complete the controlled phase. Data from the controlled phase will be cleaned and locked at data point level. The study will be unblinded and the controlled phase analyses will be performed. Efficacy and safety summary tables will be displayed by treatment group of CSB-001 or Vehicle.

Following completion of the last subject in the open-label, uncontrolled phase, efficacy and safety analyses based on the safety analysis set of the uncontrolled phase will be performed for the uncontrolled phase. Efficacy and safety summary tables will be displayed as a single treated group.

#### **7.2 Baseline and Visit Windows**

Baseline for the controlled phase is defined as the last non-missing assessment prior to the dosing of the study treatment. Baseline for the uncontrolled phase is defined as the last non-missing assessment prior to the dosing of the study treatment in the uncontrolled phase.

Analyses will be performed according to the scheduled visits.

---

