**6.3. Early Exit/Study Discontinuation**

Listed below are the procedures required for subjects exiting the study prematurely prior to the Week 8 Visit (in both controlled and uncontrolled treatment phases). Only assessments not completed or conducted as part of a planned or unscheduled study visit on the same day that the subject exits the study are required to be performed. Site personnel should make all efforts to bring the subject back to the site to complete the exit procedures.

1. Collect all test articles (used and unused)
2. Record any changes in concomitant medications/therapies
3. Record any adverse events since the last visit
4. Assess test article compliance (including collection of used BFS vials, accountability of test articles, and review of subject diary)
5. Perform logMAR pinhole distance VA OU (if study eye has been assessed at the same visit, only perform in the non-study eye)
6. Perform slit-lamp exam OU (if study eye has been assessed at the same visit, only perform in the non-study eye)
7. Perform IOP OU (if study eye has been assessed at the same visit, only perform in the non-study eye)
8. Perform dilated ophthalmoscopy OU (if study eye has been assessed at the same visit, only perform in the non-study eye)
9. Perform urine pregnancy test (on female subjects of childbearing potential)
10. Exit subject from the study

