#### **6.4.        Unscheduled Visit**

Unscheduled visits can be used for assessment of an adverse event or at the discretion of the investigator prior to a subject's next scheduled study visit. Procedures and examinations conducted at the Unscheduled Visit are at the discretion of the investigator.

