## Protocol CSB-C20-003

### Claris Biotherapeutics, Inc.

Confidential

 Subjects whose cornea is healed at Week 8 will be assessed for sustained healing at Week 10. Subjects whose cornea is not healed at Week 8 will be unmasked; subjects in the CSB-001 arm will exit the study, subjects in the vehicle arm are eligible to enter the uncontrolled treatment phase and receive an 8-week course of treatment with CSB-001.

 Subjects whose cornea is completely healed at Week 8 and sustained until Week 10 will exit the study. Subjects whose cornea is not healed at Week 10 will be unmasked; subjects in the CSB-001 arm will exit the study, subjects in the vehicle arm are eligible to enter the uncontrolled treatment phase and receive an 8-week course of treatment with CSB-001.

 Ensure exit procedures are conducted at the time of study exit for subjects exiting prior to the Week 8 Visit. Only assessments not conducted as part of a planned or unscheduled study visit at the time of study exit should be performed.

 Record adverse events after test article instillation on Day 0

 Ocular tolerability assessment to be conducted immediately after in-office study drug instillation at specified visits

 V/A and slit-lamp will be assessed in both the study and non-study eyes in the initial safety phase (i.e., first 12 subjects randomized).

 At Day 0, corneal sensitivity assessed using a cotton wisp will be performed to determine study eligibility. Corneal sensitivity will also be assessed using a Cochet-Bonnet aesthesiometer if available at the site. At Week 8, sensitivity will only be assessed in subjects at clinical sites with access to a Cochet-Bonnet aesthesiometer.

 Administer first dose in the clinic

Open-Label Uncontrolled Treatment Phase												
(Subjects randomized to vehicle in the controlled treatment phase whose cornea is not healed at Week 8 or whose cornea is healed at Week 8 but not sustained for two weeks until Week 10 are eligible to receive an 8-week course of treatment with CSB-001)												
Study Procedures	Day 0 1* Entering at Wk 8 Controlled Visit	Day 0 1* Entering at Wk 10 Controlled Visit	Wk 1	Wk 2	Wk 3	Wk 4	Wk 5	Wk 6	Wk 7	Wk 8 	Wk 10 	Early Exit 
Previous/Change in Medical History and Concomitant Meds (Systemic and Ocular)			X	X	X	X		X		X	X	X

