### 7.3 Summary Statistics

- Continuous endpoints will be summarized using descriptive statistics (number of subjects, mean, standard deviation [SD], median, minimum and maximum values). The summary statistic n will be the number of subjects with non-missing values. All means and medians will be reported to one more significant digit than the values being analyzed. Standard deviations will be reported to two more significant digits than the values being analyzed. The minimum and maximum will be reported to the same number of significant digits as the values being analyzed.
- Categorical endpoints will be summarized as the number and percentage of participants per category. Percentages will be out of the number of subjects in the population being reported, unless otherwise noted. All percentages will be rounded to one decimal point. The number and percentage of subjects will always be presented in the form XX (XX.X) where the percentage is in parentheses. To ensure completeness, all summaries for categorical and discrete variables will include all categories, even if none of the subjects had a response in a particular category. Denominators for each analysis will be based on the population of interest (e.g., safety analysis set; subjects with non-missing data).
- Time to event endpoints will be summarized using Kaplan-Meier method by treatment group. Confidence intervals for the 25th, 50th and 75th percentiles will be reported, where appropriate.
- Subject listings of data will be presented for all enrolled subjects unless specified otherwise.

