**10.4 Dilated Fundus Ophthalmoscopy**

Dilated fundus ophthalmoscopy data will be summarized by visit and by eye, and a subject listing will be presented.

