**10.6 Ocular Tolerability Questionnaire**

Ocular tolerability questionnaire data will be summary by visit and a subject listing will be presented.

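### Slit-lamp, fundus and tolerability data are summarised only by scheduled visit, so unscheduled exams have no row, early-exit exams have no assigned place, and later tolerability rows describe only subjects still dosing

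*SAP*

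**What the plan says.** - **Visit rule.** SAP 7.2 has visit windows in its title but defines none. It says: "Analyses will be performed according to the scheduled visits". It gives no rule for placing early-exit or unscheduled data.
- **Safety summaries.** SAP 10.4: "Dilated fundus ophthalmoscopy data will be summarized by visit and by eye, and a subject listing will be presented". SAP 10.2 treats slit-lamp data the same way. SAP 10.6: "Ocular tolerability questionnaire data will be summary by visit and a subject listing will be presented". None of the three has a worst, last or any-post-baseline summary.
- **Denominators (SAP 7.3).** For continuous data: "The summary statistic n will be the number of subjects with non-missing values". For categorical data: "Percentages will be out of the number of subjects in the population being reported, unless otherwise noted". The same bullet then names both the safety set and subjects with non-missing data as possible denominators, without choosing one per table. SAP 7.4 allows no imputation outside the primary endpoint except for dates.
- **Exams at early exit.** Protocol 6.3 requires slit-lamp and dilated fundus exams of both eyes for subjects leaving before Week 8. The tolerability questionnaire is not on that list.
- **Unscheduled exams.** Protocol 6.4: "Unscheduled visits can be used for assessment of an adverse event or at the discretion of the investigator". What is examined is left to the investigator.
- **Tolerability.** Footnote 6 to Table 2 of the protocol: "Ocular tolerability assessment to be conducted immediately after in-office study drug instillation at specified visits". The table marks Day 0, Week 4 and Week 8.
- **Status of these data.** SAP 2.1.1 makes the comparison of safety part of the primary objective and names slit-lamp, fundus and tolerability among its measures. Protocol 13.4 also promises summaries of change from baseline for safety parameters. SAP 10.2 and 10.4 do not mention these, and SAP 1.0 says the SAP takes precedence.

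**The concern.** Early-exit and unscheduled exams are the ones most likely to have been done because something was wrong. A table built only on scheduled visits gives them no clear place, and no other table compares the arms on them.

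Tolerability has a related problem of selection. A subject who stops the drops has no in-office dose to rate. The Week 4 and Week 8 rows are therefore conditional on having tolerated treatment that far. If one arm is tolerated less well and more of its subjects stop, those rows can make the arms look alike. At stake is how far the randomised safety comparison can be relied on. Efficacy is not involved.

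**Working it through.** **1. Which exams have a row.** From Table 2 of the protocol and Appendix 1 of the SAP, controlled phase:

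| Assessment | Scheduled | Early exit | Unscheduled |
|---|---|---|---|
| Slit-lamp, study eye | Day 0, Weeks 1, 2, 3, 4, 6, 8, 10 | yes | at discretion |
| Slit-lamp, non-study eye | Day 0, Week 8 (also Week 1 in the first 12 subjects) | yes | at discretion |
| Fundus, both eyes | Day 0, Week 8 | yes | at discretion |
| Tolerability | Day 0, Week 4, Week 8 | no | not tied to a dose |

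Early Exit is a column in the SAP's schedule; an unscheduled visit is not. For a subject leaving before Week 8, the exit exam is the only required post-baseline fundus result. After the first 12 subjects, the same holds for the slit-lamp exam of the non-study eye.

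**2. How many subjects.** Inputs from SAP 4.0 and 5.0: 128 randomised (64 per arm), 96 to complete, dropout about 10%.

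- Dropout alone: 0.10 × 128 = 12.8, about 13 subjects, or about 6 per arm.
- The plan's own inflation: 96 / 0.90 = 106.7, so 107 would cover dropout. Randomising 128 implies a total loss of 1 − 96/128 = 25%. The plan puts the excess down to inadequate images, so 25% is only an outer bound on early leaving.

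Thirteen is an upper figure at 10% dropout. It assumes that every dropout leaves before Week 8 and attends an exit exam. Subjects lost to follow-up may have no exit exam.

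**3. What exit exams could add.** The documents give no finding rates. Assume that about 5% of those remaining at Week 8 have a finding, and let none, half or all of the leavers have one at exit. Per arm of 64:

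| Leavers | Week 8, non-missing | Any exam: none | half | all |
|---|---|---|---|---|
| 3 (5%) | 3/61 = 4.9% | 3/64 = 4.7% | 5/64 = 7.8% | 6/64 = 9.4% |
| 6 (10%) | 3/58 = 5.2% | 3/64 = 4.7% | 6/64 = 9.4% | 9/64 = 14.1% |
| 16 (25%) | 2/48 = 4.2% | 2/64 = 3.1% | 10/64 = 15.6% | 18/64 = 28.1% |

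Half of 3 is taken as 2. If leavers have no findings, nothing is lost.

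**4. Tolerability under each denominator.** Assumed, not from the documents: 6 of 64 CSB-001 and 2 of 64 vehicle subjects stop before Week 4 for ocular intolerance, and about 5% of those continuing give the worst rating (3 per arm).

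| Week 4 table | CSB-001 | Vehicle | Difference |
|---|---|---|---|
| Non-missing | 3/58 = 5.2% | 3/62 = 4.8% | 0.3 points |
| Safety set | 3/64 = 4.7% | 3/64 = 4.7% | 0 |
| Stopped, as its own category | 6/64 = 9.4% | 2/64 = 3.1% | 6.3 points |
| Worst rating or stopped | 9/64 = 14.1% | 5/64 = 7.8% | 6.3 points |

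The non-missing denominator leaves out those who stopped. The safety-set denominator counts them, without saying so, as not having a bad rating. With equal stops, say 4 per arm, the rows read 3/60 = 5.0% in both arms. The comparison is then fair, and only the level is understated.

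**The case against.** A reader might infer that the SAP excludes early-exit exams. It does not say so. The sentence in 7.2 can be read as using nominal visits in place of derived day windows. Early Exit has its own column in Appendix 1, so a by-visit table could carry an Early Exit row. Leaving an early exit exam out of the Week 8 row would in itself be right.

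A reader might also infer that only non-missing values count. That sentence in SAP 7.3 belongs to continuous data. Slit-lamp and fundus findings are naturally categorical, and there the default is the reported population, with the final choice left open.

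Nor do subjects who stop vanish. Their Day 0 rating and every visit they attended stay in the tables, and Protocol 8.1 encourages them to complete the remaining visits. SAP 10.1 tabulates ocular TEAEs by eye, and TEAEs leading to treatment discontinuation. SAP 8.1 reports reasons for discontinuation, and listings cover all enrolled subjects.

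All of this stands, and it limits the point without removing it. An Early Exit row, if produced, would still give no cumulative rate by arm and would not hold unscheduled exams. Attending Week 8 off treatment yields a fundus exam but no tolerability rating, because the questionnaire follows a dose. AE tables pick up an exam finding only if it is reported as an AE, and listings do not compare arms. The tolerability gap comes from the protocol's schedule as much as from SAP 7.2, so no visit-mapping rule can recover ratings that were never taken.

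**Conclusion.** The point holds as a gap in specification and summary. Unscheduled exams enter no summary table. Early-exit exams are not assigned to one. There is no any-post-baseline comparison by arm. Tolerability at Weeks 4 and 8 is conditional on still dosing.

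The number whose only post-baseline fundus result could be affected is at most about 13 of 128 at 10% dropout, and fewer if some leavers have no exit exam. The percentages in steps 3 and 4 rest on assumed finding rates and an assumed 6-versus-2 split of stops. They show how the tables would behave and do not predict a result. The documents do not support saying that exit data are excluded, or that the summaries will favour CSB-001: a distorted comparison needs unequal stopping, and nothing in the plan says which arm would stop more.

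The primary efficacy test is unaffected. The change is worth making because the safety comparison is part of the primary objective.

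**What to change.** Keep the by-visit rows and add two things.

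1. **SAP 7.2, 10.2 and 10.4.** For each eye and arm, report the number and percentage of safety-set subjects with any worsening from baseline at any controlled-phase exam, including early-exit and unscheduled visits, cut off at the first open-label dose. Define worsening from the categories recorded on the CRF, for example normal to abnormal, since the protocol names the structures but gives no grading scale. Also state whether Early Exit is shown as its own row. Some exams are done at Week 10 only in vehicle subjects entering the open-label phase (Protocol 6.2.1.2). Say whether these count, because the CSB-001 arm has no counterpart. The new row would also go some way to restoring the change-from-baseline summaries in Protocol 13.4.

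2. **SAP 10.6.** At Weeks 4 and 8, use the safety set as denominator and add a category for subjects who stopped test article before that visit because of an ocular adverse event, with stops for other reasons shown separately. Take it from the recorded reason for discontinuation. For subjects who stop treatment but stay in the study, the action taken for each AE (Protocol 12.1) should supply it. The CRF is not among the documents, so confirm that these fields are available.

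The cost is SAP wording and a few table rows, with no new procedure. The any-exam row includes exams done for cause, so its rates will be slightly less favourable than those at scheduled visits. The second item partly repeats the TEAE discontinuation line, but puts it where the tolerability rows are read. Neither item recovers ratings that were never collected.

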### 7.3 Summary Statistics

- Continuous endpoints will be summarized using descriptive statistics (number of subjects, mean, standard deviation [SD], median, minimum and maximum values). The summary statistic n will be the number of subjects with non-missing values. All means and medians will be reported to one more significant digit than the values being analyzed. Standard deviations will be reported to two more significant digits than the values being analyzed. The minimum and maximum will be reported to the same number of significant digits as the values being analyzed.
- Categorical endpoints will be summarized as the number and percentage of participants per category. Percentages will be out of the number of subjects in the population being reported, unless otherwise noted. All percentages will be rounded to one decimal point. The number and percentage of subjects will always be presented in the form XX (XX.X) where the percentage is in parentheses. To ensure completeness, all summaries for categorical and discrete variables will include all categories, even if none of the subjects had a response in a particular category. Denominators for each analysis will be based on the population of interest (e.g., safety analysis set; subjects with non-missing data).
- Time to event endpoints will be summarized using Kaplan-Meier method by treatment group. Confidence intervals for the 25th, 50th and 75th percentiles will be reported, where appropriate.
- Subject listings of data will be presented for all enrolled subjects unless specified otherwise.

### 7.4 Data Handling Rules

There will be missing data imputation for the primary efficacy analysis. See primary efficacy analysis [Section 9.1](#) for details.

Besides the imputations for the primary endpoint, there will be no imputation of missing data other than for partial or missing dates where complete dates are required to flag data as treatment-emergent or concomitant with treatment. Partial/missing start and end dates for AEs and concomitant medications will be imputed as follows.

Partial/missing start date:

- Dates with missing day only will be imputed as the 1st of the month unless the month and year are same as the month and year of first dose of study medication, in which case missing day will be imputed as the first dose day of study medication.
- Dates with both day and month missing will be imputed as 1 Jan unless the year is same as the year of first dose of study medication, in which case missing day and month will be imputed as the first dose day and month of study medication.

- 
- Completely missing dates will be imputed as the first dose date of study medication unless the end date is on or before the first dose date of study medication, in which case missing date will be imputed as 1 Jan of the same year as the end date.

Partial/missing end date:

- Dates with missing day only will be imputed as the last day of the month.
- Dates with both day and month missing will be imputed as 31 Dec.
- If the ongoing flag is missing or “Yes” then the date will not be imputed unless death date is available, in which case the missing date will be imputed as the death date. If ongoing is “No” then the missing end date will be imputed as the last dose date.
- If the imputed date is after the date of death, then the end date will be set equal to the date of death.
- The original dates will be displayed in data listings and the imputed dates will be used in derivations only (study day, treatment-emergence status, etc.).

Partial/missing start dates for initial and current NK stage will be imputed as follows.

- Dates with missing day only will be imputed as the 16th of the month.
- Dates with both day and month missing will be imputed as 1 July.
- Completely missing dates will not be imputed. The current NK stage duration will be left as missing.

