### 3.0 STUDY DESIGN

This is a multi-center, randomized, double-masked, vehicle-controlled, parallel-group safety and efficacy study.

[figure not shown]
Approximately 128 subjects with stage 2 or 3 NK will be randomized in a 1:1 ratio to the CSB-001 investigational treatment arm or vehicle control arm at approximately 50 investigative sites in the United States and Canada. All subjects will provide written informed consent prior to the conduct of any study procedures at the Day 0 Screening/Randomization Visit. Subjects must meet all study inclusion and exclusion criteria to qualify for enrollment in the study. Subjects will be required to discontinue all topical ophthalmic medications and contact lens use (both therapeutic and for refractive correction) in the study eye as noted in the exclusion criteria upon enrollment. The only exceptions are the allowance for use of preservative-free antibiotic eye drops if prescribed by the investigator and/or a non-preserved IOP-lowering topical ocular drop (with the exception of timolol) administered once-daily over the course of the study.

An initial safety phase is included whereby the first 12 randomized subjects will be evaluated by the masked Medical Monitor for dose limiting safety findings. Each subject will be assessed within three days of the Week 1 Visit. In the absence of an adverse event assessed as a dose limiting finding, enrollment of the remaining subjects will commence.

All subjects will dose with the randomized treatment QID for 8 weeks (referred to as the controlled treatment phase which includes the above initial safety phase). During the controlled treatment phase, subjects will return to the clinic weekly from Day 0 to Week 8, and again at Week 10. Subjects randomized to vehicle who are not healed at Week 8 or who are healed at Week 8 but do not remain healed at the Week 10 Visit are eligible to receive an 8-week QID course of CSB-001 (referred to as the uncontrolled treatment phase). See Schedule of Assessments, [Appendix 1](#).

Subjects will be followed as described below based on the randomized treatment arm and Week 8 and/or Week 10 investigator assessment of corneal healing. Subjects whose cornea is not healed (deemed non-responders) at the Week 8 or Week 10 Visit will be unmasked. See Schematic of Study Design, [Figure 1](#).

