### **8.4 Prior and Concomitant Medications**

Prior and concomitant medications will be coded with the World Health Organization Drug Dictionary (WHO-DD), and summarized by drug class (Anatomical Therapeutic Chemical [ATC] Level 3) and preferred term; a subject will be counted only once for each medication.

Concomitant medications are medications which started 1) prior to initiation of study treatment administration and continuing for any period of time following the Day 0 administration of study treatment or 2) at any time following the Day 0 administration of study treatment. Prior medications are medications which are started before the Day 0 administration of study drug.

All medication will be listed with the prior medications flagged. Systemic prior and concomitant medication, and ocular prior and concomitant medication will be summarized separately. Ocular prior and concomitant will be summarized by study eye and non-study eye.

---

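### SAP 7.4 sets a partial medication start date to the first-dose date even when a known stop date is earlier, so the start can fall after the stop and the drug loses its prior status

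*SAP*

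**What the plan says.** SAP 7.4 (Data Handling Rules) has three rules for incomplete start dates of adverse events and concomitant medications.

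- Day missing: first of the month, unless month and year are those of first dose, "in which case missing day will be imputed as the first dose day of study medication".
- Day and month missing: 1 January, unless the year is that of first dose, "in which case missing day and month will be imputed as the first dose day and month of study medication".
- Completely missing: the first-dose date, "unless the end date is on or before the first dose date of study medication"; in that case 1 January of the stop year.

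Only the third rule consults the stop date. SAP 7.4 adds that listings show dates as recorded and that imputed dates serve derivations only.

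SAP 8.4 then classifies: "Prior medications are medications which are started before the Day 0 administration of study drug". A medication is concomitant if it began earlier and continued for any time after the Day 0 administration, or if it began following that administration. All medications are listed with the prior ones flagged, and ocular medications are tabulated by study and non-study eye.

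Protocol 7.4 collects everything taken in the 3 months before Day 0. SAP 3.0 requires treatments to end at entry, with two named exceptions: "Subjects will be required to discontinue all topical ophthalmic medications and contact lens use" in the study eye. Stops at or shortly before Day 0 are therefore expected in these data.

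**The concern.** Moving an uncertain start to the first-dose date is a common precaution: if a drug might have begun on treatment, count it as on treatment. That reasoning fails when the record itself shows that the drug stopped before the first dose. The imputed start then contradicts a recorded date, and the interval runs backwards.

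The SAP guards against this where it knows least (no start date at all) but not where it knows more (month or year). So a record with more information can be handled worse than one with less.

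At stake is the sorting of pre-study treatments, including earlier ocular therapy in the study eye, into the prior and concomitant medication summaries, and the prior flag in the listing.

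**Working it through.** The plan states no figure on this point, so there is none to reproduce. The check is to apply the rules to example records.

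**Inputs.** Start-date and end-date rules from SAP 7.4; classification from SAP 8.4. Assumed first dose: 20 June 2023.

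**Step 1: the rules as written.** Where the stop is itself partial, it is completed first by its own rule.

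| Recorded start | Recorded stop | Start under SAP 7.4 | Result |
|---|---|---|---|
| June 2023, day missing | 10 June 2023 | 20 June 2023 | start 10 days after stop |
| 2023 only | 15 April 2023 | 20 June 2023 | start 66 days after stop |
| 2023 only | April 2023, day missing (becomes 30 April) | 20 June 2023 | start 51 days after stop |
| completely missing | 15 April 2023 | 1 January 2023 | valid, prior only |
| May 2023, day missing | 10 June 2023 | 1 May 2023 | valid, prior only |
| 2022 only | 10 June 2023 | 1 January 2022 | valid, prior only |

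The second and fourth rows have the same stop date. The record with the year of start comes out wrong, and the one with no start at all comes out right.

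**Step 2: classification of the first three rows.** The imputed start equals Day 0, so it is not before the Day 0 administration and the drug is not prior. It cannot be concomitant as an earlier drug that continued. Whether it is concomitant as a drug begun following the administration depends on whether a date equal to Day 0 counts. If it does, the drug is concomitant. If not, the drug is in neither category. Both are wrong for a drug that stopped before Day 0.

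**Step 3: how often, among records of this kind.** Take every first-dose day in 2023, every true start 1 to 90 days earlier, and every complete stop from the start to Day 0, all equally weighted (an assumption). The number of combinations is 365 × Σ(a + 1) for a = 1 to 90, which is 365 × 4,185 = 1,527,525.

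| What is missing from the start | Moved to Day 0 | Start after stop |
|---|---|---|
| Day only | 4.0% | 3.7% |
| Day and month | 83.6% | 81.7% |

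The difference between the two columns is records that stop on Day 0 itself. These are shares of records that already have that type of partial start, not of all medication records. Drugs begun more than 90 days before Day 0 would lower them, because their start month or year less often matches first dose.

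**Step 4: the rules with the stop-date check added.** If the stop is before first dose, use the first of the month or 1 January. The three faulty rows become starts of 1 June, 1 January and 1 January 2023. All three intervals are valid and all three drugs are prior only.

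**Step 5: a stop on Day 0.** Start 2023 and stop 20 June 2023 become a one-day interval on 20 June. It does not run backwards, but the drug is no longer prior. Whether it is concomitant turns on time of day, which a date does not settle.

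**The case against.** The best defence is that little depends on these dates. No efficacy endpoint uses them. Listings keep the recorded dates, so anyone reading the listing sees that the drug stopped before Day 0, although its prior flag may be missing. Complete dates are unaffected, and so are partial starts from an earlier month or year when the stop is complete. Protocol 14.1, 14.3 and 14.6 provide queries, validation checks and source verification that should limit incomplete dates. All of this stands, and it keeps the point minor. It does not make the rule correct.

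A reader might infer more than the documents support:

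- *That discontinuation at entry can no longer be verified from the tables.* The tables count subjects by drug class and preferred term. Even with complete dates they could not verify it, since the permitted antibiotic and pressure-lowering drops count as concomitant, as does any drug continued briefly after the Day 0 dose.
- *That the per-protocol set is affected.* SAP 6.3 and 8.5 base exclusion on recorded protocol deviations reviewed before lock and unblinding. Nothing derives deviations from imputed medication dates.
- *That the end-date rules share the fault.* SAP 7.4 says that for a drug marked not ongoing with no stop date, "then the missing end date will be imputed as the last dose date". This can class a drug stopped before Day 0 as concomitant, but there the stop is unknown, and counting the drug as possibly on-study is a defensible conservative choice. A drug with a known earlier start also stays prior. A refinement based on the visit at which the record was collected would need a field that these documents do not show.

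**Conclusion.** The point holds for one rule in two forms: a start missing its day in the month of first dose, and a start missing day and month in the year of first dose, each with a known stop before Day 0. These records get an impossible interval and lose prior status. Whether they also become concomitant is not settled by SAP 8.4.

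The conclusion rests on the wording of SAP 7.4 and 8.4 alone. The shares in the working also rest on equal weighting of days, starts within 90 days of Day 0 and complete stop dates. The actual number of affected records is not in the documents and could be small. The effect is confined to the medication summaries and the prior flag. Wrong as written; minor.

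**What to change.** In SAP 7.4, add to both partial-start rules, for medications: if the stop date (completed by its own rule where partial) is before the first-dose date, impute the first of the month when only the day is missing, or 1 January when day and month are missing. Such a drug is then prior only.

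In SAP 8.4, state how a medication whose start or stop date is Day 0 itself is classified. Protocol 7.4 collects medication dates and does not mention times, and stops on Day 0 are foreseeable because discontinuation is required at enrolment. The existing check for completely missing starts includes a stop on the first-dose date, so its boundary should agree with whatever is stated. A stop on Day 0 should not simply be labelled prior only, because SAP 8.4 makes a drug concomitant if its use continued after that day's dose.

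The cost is one clause in each of two rules, one sentence in SAP 8.4 and a small programming change. No new data are needed.
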